5.2.3 Summary of Clinical and Nonclinical Studies

This is a summary of nonclinical and clinical studies. More detail is provided in the Investigator Brochure.

A series of nonclinical studies were conducted in mice to assess the effect of A3907 on bile acid homeostasis. The studies showed a dose-dependent increase in faecal total bile acid levels confirming ABST inhibition in the ileum. In addition, increases in serum 7 α -hydroxy-4-cholesten-3-one (C4) levels and decreases in serum low density lipoprotein cholesterol (LDL-C) were noted, consistent with increased hepatic bile acid biosynthesis.

Due to its systemic availability, A3907 is also anticipated to inhibit ASBT in the kidney in cholestatic conditions, resulting in reduction of bile acid pool through a net loss of bile acids

via urine. Urine primary and secondary bile acid concentrations were significantly, and dose dependently elevated by A3907 treatment in mice.

In addition, A3907 treatment is expected to reduce ASBT mediated bile acid transport within the bile ducts and protect against bile acid induced hepatic cell damage. In in vitro assays, A3907 directly inhibited ASBT and reduced bile acid induced-cholangiocyte proliferation and apoptosis, which are characteristic features of cholestatic liver disease. A3907 treatment has also shown positive effects on biomarkers and liver histology in animal models of cholestatic liver disease. The systemic bioavailability after oral administration of A3907 in mice, rats, and dogs was estimated to be approximately CCI. The time to maximum plasma concentration (T_{max}) was approximately CCI and the apparent terminal elimination half-life ($t_{1/2}$) was approximately CCI. The maximum plasma concentration (C_{max}) increased after increasing oral doses suggesting dose-dependent pharmacokinetics (PK).

Secondary pharmacology and an International Council on Harmonization of Technical Requirements for Pharmaceuticals for Human Use (ICH) S7 core of in vitro and in vivo safety pharmacology studies evaluating A3907 doses up to CCI mg/kg/day showed no adverse effects of concern, and toxicology studies showed that A3907 had a tolerable safety profile. CCI

CCI

A3907 showed no genotoxic potential invitro and administration to pregnant rats and rabbits during organogenesis in preliminary embryo foetal development studies showed no adverse effects on foetal survival, growth, or development.

In a first-in-human (FIH) study (Study A3907-001), A3907 or matching placebo were administered in capsules to healthy subjects as single oral doses of C to C mg or CCI oral doses of CCI mg for 7 days. Overall, A3907 was well tolerated when administered as single and multiple ascending doses (SAD/MAD) to the healthy subjects. There were no serious adverse events (SAEs), all treatment-emergent adverse events (TEAEs) were mild in

severity, and no subjects discontinued study drug or withdrew from the study due to TEAEs. The only treatment-related AEs that occurred in ≥ 2 subjects following single or multiple doses of A3907 were diarrhoea, abdominal pain, and headache. Pharmacokinetic analysis revealed that, with this formulation, A3907 was slowly absorbed (T_{\max} approximately [REDACTED] hours) and dose proportionality was demonstrated at single doses of [REDACTED]; the higher single dose of [REDACTED] mg did not result in increased exposure. No accumulation was seen following multiple [REDACTED] doses of [REDACTED] mg for 7 days, consistent with a half-life of approximately [REDACTED] hours. An increase in serum C4 concentrations and a decrease in serum LDL-C concentrations was observed at all A3907 doses; exploratory PK/pharmacodynamics (PD) results suggested a weak correlation between these PD parameters and A3907 PK parameters. While no clear trends were seen between A3907 concentrations and serum total bile acid concentrations, there was a decrease in total urine bile acids excreted at all treatment doses compared to placebo. Together, results of this study suggest that A3907 does inhibit ASBT but the net effect in the intended population is yet to be determined.

5.3 Rationale

A3907 is under development as an oral treatment of cholestatic liver disease, including PSC.

As there is no known medical treatment that slows disease progression, this remains an unmet medical need for patients with PSC. Disease progression is influenced by altered bile acid flow due to biliary complications often observed in patients with PSC, which also contributes to symptoms such as pruritus. Modifying the circulating bile acid pool and reducing the bile acid load may, therefore, have positive effects on PSC disease progression and symptoms.

A3907 is a systemically available, potent, selective inhibitor of the ASBT that has been shown to inhibit both intestinal, renal, and bile duct bile acid transport:

- Pharmacological inhibition of intestinal ASBT by A3907 leads to a net loss of bile acids via faeces.,
- Due to its systemic availability, A3907 is also anticipated to inhibit ASBT in the kidney in cholestatic conditions, resulting in reduction of circulating bile acids through a loss of bile acids via urine.

- Treatment with A3907 is expected to reduce ASBT -mediated bile acid transport within the bile ducts and protect against bile-acid induced hepatic cell damage. This is supported by positive effects demonstrated on biomarkers and liver histology in animal models of cholestatic liver disease and reduction in bile acid induced cholangiocyte proliferation and apoptosis, which are characteristic features of cholestatic liver disease.

5.4 Dose Rationale

A3907 has been extensively evaluated in nonclinical studies and has been shown in vitro and in vivo to effectively inhibit ASBT. The dose selected for this study is based on data collected in nonclinical studies, as well as safety data generated from the FIH study (A3907-001).

In Study A3907-001, A3907 in a capsule formulation was administered to healthy subjects in single doses (SAD) ranging from ■ mg to ■■■ mg, and multiple doses (MAD) ranging from ■■■ up to ■■■ for 7 days. Administration of A3907 was well tolerated after single and 7-day repeated doses, and there were no clinically relevant safety findings at any of the dose levels. In the SAD study, the geometric mean of C_{max} and AUC were ■■ ng/mL and ■■ ng h/mL respectively, and the highest C_{max} and AUC values were ■■ ng/mL and ■■ ng h/mL respectively. In the MAD study, a mean C_{max} of ■■ ng/mL and AUC of ■■ ng h/mL was observed at the ■■ dose at steady state. Pharmacodynamic effects were observed with an increase in C4, a biomarker of bile acid synthesis; a reduction in LDL-C; and a post-prandial increase in serum bile acids at all A3907 dose levels administered for 7 days.

In this 12-week study, A3907 doses of 10 and 30 mg QD (Arms 1 and 2, respectively), and 30 mg BID (Arms 3 and 4) in a tablet formulation will be administered to 6 patients per arm.

■■■

■■■

These doses are expected to result in exposures predicted to be pharmacodynamically active based on pre-clinical mouse disease models. A3907 has been administered orally for three months to rats and dogs in toxicology studies at doses up to ■■ mg/kg/day, respectively, with no adverse findings at any of the dose levels explored. ■■■

CCI

CCI

). In this study, individual PK values may vary due to factors such as gastrointestinal transit time, presence of food, volume of contents within the gastrointestinal tract, and liver impairment. Additionally, A3907 will be administered in a tablet formulation. CCI

CCI

To mitigate risks related to potential variability in PK, patients will first receive a single daily dose of A3907 (10 mg once daily [QD] in Arm 1, 30 mg QD in Arm 2, or 30 mg twice daily [BID] in Arms 3 and 4). After review of each patient's PK data, if the systemic exposures do not exceed the highest systemic exposure previously established in the single dose part of Study A3907-001, CCI the dose will be confirmed, and the patient will begin administration of A3907 QD or BID for 12 weeks. If the exposures exceed the highest systemic exposure previously achieved in healthy subjects in the SAD part of Study A3907-001, individual patients will be terminated early.

5.5 Risk/Benefit Assessment

Risk assessment

A3907 has been administered to 56 healthy subjects in the FIH study (A3907-001). This study demonstrated that A3907 was well tolerated at a dose of up to CCI in the SAD study and CCI (capsule formulation) administered daily for CCI in healthy subjects in the MAD study. The potential risks to study participants associated with A3907 are described in the Guidance to Investigator section of the Investigator's Brochure. The most common A3907-related AEs in the FIH study were diarrhoea, abdominal pain, and headache.

Pharmacokinetic analysis revealed that A3907 was slowly absorbed (T_{max} approximately CCI c hours) and dose proportionality was demonstrated at single doses of CCI; a slightly less than dose proportional- increase was observed with multiple doses of CCI to CCI for 7 days. Repeat doses of A3907 resulted in CCI

in the SAD study, and [CCI] in the MAD study. Nonclinical secondary and safety pharmacology studies, general toxicity studies, and in vitro genotoxicity studies have also been conducted with no adverse effects of concern identified. Nonclinical toxicology studies of A3907 showed no signs of acute toxicity following single repeated oral dosing in rats and dogs up to a dose of [CCI] mg/kg/day and [CC] mg/kg/day, respectively, for up to 13 weeks. Elevated ALP and/or ALT values were observed at a dose of [CCI] mg/kg/day in the 7- and 14-day repeat dose studies in the dog; however, the elevations were fully or almost fully reversed at the end of the recovery phase. Elevations in liver enzymes were not observed in the 13-week dog study or the FIH study.

This is the first time A3907 will be administered to patients with PSC. Potential risks in the patient population are unknown. The potential risks associated with A3907 treatment will be mitigated by routine monitoring as noted in [Section 9.3](#). The study has been designed with a lead-in period to determine the exposure of A3907 in individual patients to ensure that exposure levels observed at the highest dose level in A3907-001 are not exceeded. Additionally, enrollment into Arm 2 will only begin after at least 3 patients in Arm 1 have completed 2 weeks of treatment at the lower dose and an SRC has reviewed safety and PK data ([Section 10.2.5](#)). For Arms 3 and 4, enrollment will only begin after at least 3 patients in Arm 2 have completed 2 weeks of treatment at the 30 mg dose QD dose, and an SRC has reviewed safety and PK data ([Section 10.2.5](#)). The SRC will also review safety data from this study on an ongoing basis and after the last patient reaches 12 weeks. Thus, exposure of patients in this study is justified by the anticipated benefits that may be afforded to the wider population of patients by continued development of A3907.

Benefit assessment

This study is designed to evaluate the safety, tolerability, PK, and PD of A3907 in patients with PSC. The dose selected is expected to reduce bile acid transport, leading to a decrease in serum bile acids, and positively influence liver enzymes and markers of liver fibrosis. It is not known whether patients participating in this study will benefit from the treatment. Due to the short duration of this study, any benefit observed is not expected to persist beyond the end of the study. However, the increased understanding of the effects of A3907 in this population may potentially result in new treatment options that would ultimately benefit patients with PSC.

5.5.1 Risk/Benefit of Receiving COVID-19 Vaccine during Trial Participation

Nonclinical: Bile acids in general are not expected to perturb immunological responses. No signs of immunological reactions have been seen in clinical studies thus far. Based on the outcome from the standard toxicity studies and the general profile and mechanism of action of A3907, the risk of immunotoxicity has been considered low and dedicated immunotoxicity studies have not been performed.

Clinical: The FIH study did not report any safety signal or trends relative to immunological reactions, which was consistent with the nonclinical data. No trends or safety signals were observed as it relates to haematology including white blood cell count, differential counts, and C-reactive protein. No events of allergic reactions to A3907 or its excipients have been reported.

The risk of an undesirable outcome after receiving the COVID-19 vaccine while treated with A3907 has not been studied and is unknown.

6 STUDY OBJECTIVES AND ENDPOINTS

6.1 Study Objectives

6.1.1 Primary Objectives

The primary objective of this study is to evaluate the safety and tolerability of A3907 in patients with PSC with and without a CRS following repeat doses.

6.1.2 Secondary Objectives

The secondary objectives are:

- To evaluate the PK of A3907
- To evaluate the effect of A3907 on bile acid levels
- To evaluate the effect of A3907 on liver health
- To evaluate the effect of A3907 on bile acid synthesis

6.1.3 Exploratory Objectives

The exploratory objectives are:

- To explore the effect of A3907 on markers of liver inflammation and fibrosis
- To evaluate the effect of A3907 on symptoms
- To explore the effect of A3907 on episodes of cholangitis (for patients with available 12-week data prior to dosing)

Additional Exploratory Objectives, Arm 4 Only:

- To evaluate the effects of A3907 on survival without a liver transplant
- To evaluate the effect of A3907 on bile duct function

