	To evaluate the effect of A3907 on symptoms	
 • Change from Baseline to Week 12 in pruritus using the daily pruritus scores captured via the Pruritus numerical rating scale (NRS) • Change from Baseline to Week 12 in fatigue using the daily fatigue scores captured via the fatigue NRS • Change from Baseline to Week 12 in sleep disturbance using the daily sleep disturbance scores captured via the sleep disturbance NRS • Change from Baseline to Week 12 in mood using the daily mood scores captured via the mood Likert scale
	To explore the effect of A3907 on episodes of cholangitis (for patients with available 12-week data prior to dosing)	Episodes of cholangitis requiring antibiotic use in the 12 weeks prior to dosing versus the 12 weeks after dosing

Name of Sponsor/Company: Albireo AB	Name of Product: A3907	Name of Active Ingredient: A3907
Exploratory Arm 4 Only	To evaluate the effects of A3907 on survival without a liver transplant	Change of MELD score from baseline to Week 12
	To evaluate the effect of A3907 on bile duct function	Change in endoscopic biliary dilation intervals/ frequency in the 12 weeks prior to study start (V2) compared to the 12--week treatment period for those subjects who are regularly dilated.

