6.2.3 Exploratory Endpoints

The exploratory endpoints are:

- Change from Baseline to Week 12 in autotaxin
- Change from Baseline to Week 12 in ProC3
- Change from Baseline to Week 12 in high-sensitivity C-reactive protein (hsCRP)
- Change from Baseline to Week 12 in matrix metalloprotease 7(MMP7) and matrix metalloprotease 9 (MMP9)
- Change from Baseline to Week 12 in enhanced liver fibrosis (ELF) and Mayo-PSC score
- Change from Baseline to Week 12 in carbohydrate antigen 19-9 (CA 19-9)
- Change from Baseline to Week 12 in liver stiffness as assessed by FibroScan
- Change from Baseline to Week 12 in pruritus using the daily pruritus scores captured via the Pruritus Numerical Rating Scale (NRS)
- Change from Baseline to Week 12 in fatigue using the daily fatigue scores captured via the fatigue NRS
- Change from Baseline to Week 12 in sleep disturbance using the daily sleep disturbance scores captured via the sleep disturbance NRS
- Change from Baseline to Week 12 in mood using the daily mood scores captured via the mood Likert scale
- Episodes of cholangitis requiring antibiotic use in the 12 weeks prior to dosing versus the 12 weeks after dosing

Additional Exploratory Endpoints, Arm 4 Only

- Change of model for end-stage liver disease (MELD) score from baseline to Week 12
- Change in endoscopic biliary dilation intervals/ frequency in the 12 weeks prior to study start (V2) compared to the 12-week treatment period for those subjects who are regularly dilated.

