AFP = (alpha-fetoprotein); C4 = (7 α -hydroxy-4-cholesten-3-one); CA 19-9 = carbohydrate antigen 19-9; ECG = electrocardiogram; ERCP = endoscopic retrograde cholangiopancreatography; ELF = enhanced liver fibrosis; EOT = End-of-Treatment; FGF-19 = fibroblast growth factor 19; FSH = follicle stimulating hormone; hsCRP = high-sensitivity C-reactive protein; MIST = metabolites in safety testing; MMP = matrix metalloproteinase; MRCP = magnetic resonance cholangiopancreatography; NRS = numerical rating scale; WOCBP = women of childbearing potential; WONCBP = women of non-childbearing potential.

- ^a The EOS visit is required 14 (+/-2 days) following Visit 7 or the date of last dose for patients who prematurely discontinue treatment.
- ^b An EOT visit must be performed as soon as possible after premature drug discontinuation. If the patient is terminated after Visit 2 due to high exposure, an End-of-Study Visit should be conducted.
- ^c Any new medical or surgical history findings after the Screening Period (Visit 1) will be reported as an AE, not as patient medical or surgical history.
- ^d To include height (Screening only), weight, temperature, pulse, and systolic and diastolic blood pressure. Vital sign measurements should be taken before A3907 administration.
- ^e The last dose of study drug is planned to be administered at Visit 7. The first of the BID doses will be administered at the clinic and patients will be instructed to take the second of the BID doses at home, 12 hours after the first dose was received.
- ^f Patients will return all unused study drug at Visit 4, Visit 5, Visit 6, and Visit 7. The study site staff will count all returned drug, assess compliance, and record drug accountability.
- ^g Patients will fast for 4 hours prior to all pre-dose blood samples.

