7.2.4 Withdrawal of Patients

7.2.4.1 Individual Study Drug Interruption and/or Discontinuation

Study drug administration will be discontinued for patients with C_{max} or AUC that exceed the safety margins observed in the FIH study ([Section 5.4](#)), or because of circumstances leading to study withdrawal as detailed in [Section 7.2.4.2](#).

A patient will discontinue dosing but may remain in the study for safety monitoring if any of the following criteria are met:

- A patient's desire to discontinue study drug for any reason.
- Any AE considered related to A3907 that in the opinion of the investigator (or designee) and sponsor's medical monitor poses a risk to the patient's safety or well-being and warrants study drug discontinuation ([Section 9.3.6](#)).
- Liver transplantation.
- Pregnancy

- A patient's exposures exceed the arm's highest systemic exposures previously achieved in healthy subject CCI

CCI

The reason and date the patient is discontinued from the treatment will be documented in the electronic case report form (eCRF). The patient will undergo End-of-Treatment and End-of-Study procedures as defined in [Table 1](#).

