7.2.4.2 Withdrawal from Study

Patients will be informed that they have the right to withdraw from the study at any time, without prejudice to their medical care, and that they are not obliged to state their reasons.

Any withdrawal, and reasons for withdrawal, must be fully documented in the eCRF and source documents and the patient followed by the investigator/investigative staff.

Withdrawn patients may be replaced, as needed, to ensure 6 patients are enrolled into the 12-week Treatment Period of each treatment arm.

Patients will be withdrawn in the following circumstances:

- A patient's desire for withdrawal for any reason.
- Lost to follow-up (every effort must be made to contact the patient; a certified letter must be sent).
- An AE which, in the opinion of the investigator (or designee), necessitates withdrawal.
- Death.
- A patient's substantial non-compliance (Patient Diary and study drug compliance) or protocol violation.
- An investigator's (or designee's) opinion that continuing the patient in the study is not appropriate. The investigator (or designee) may withdraw a patient at any time if it is considered to be in the patient's best interest.
- Liver transplantation.
- Pregnancy

The reason and the date the patient is withdrawn from the study will be documented in the eCRF and source documents. If a patient is withdrawn from the study, the investigator/investigative staff will attempt to complete all End-of-Study (Visit 8) procedures within 14 days following premature withdrawal (i.e. 14 days following the final dose of the study drug).

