10.2.2.2 Missing Data

Missing data will be reported descriptively. In general, imputations of missing observations will not be made. Any additional analysis concerning missingness and details regarding handling of missing data will be described in the statistical analysis plan (SAP).

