9.7. MELD Score

For Arm 4, the MELD score will be calculated as follows:

$$\text{MELD Score} = 9.57 \times \ln(\text{creatinine mg/dL}) + 3.78 \times \ln(\text{total bilirubin mg/dL}) + 11.2 \times \ln(\text{INR}) + 6.43$$

The MELD Na Score will be calculated as follows:

$$\text{MELD Na Score} = \text{MELD} - \text{Na (mEq/L)} - [0.025 \times \text{MELD} \times (140 - \text{Na (mEq/L)})] + 140$$

For calculation of the MELD score, laboratory values less than 1.0 will be set to 1.0 and serum creatinine values greater than 4.0 mg/dL (equivalent to 353.6 $\mu\text{mol/L}$) will be set to 4.0. For calculation of the MELD Na score, sodium (Na) values greater than 140 mEq/L will be set to 140 and values less than 125 mEq/L will be set to 125.

For Arm 4, absolute change from baseline 1 in MELD score will be presented for the Safety Analysis Set. Similar summary tables presenting absolute change from baseline 2 for the 12-week treatment period will be presented for MELD scores for patients in the Safety Analysis Set who actively entered 12-Week treatment period. Supporting listing will also be presented for the Safety Analysis Set.

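### The Arm 4 objective is transplant-free survival, but its only planned measure is change in MELD, which does not count deaths or transplants

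*Protocol*

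**What the plan says.** Protocol Section 6.1.3 lists, for Arm 4 only, "To evaluate the effects of A3907 on survival without a liver transplant". In the synopsis table the endpoint beside it is "Change of MELD score from baseline to Week 12", and Section 6.2.3 repeats it as "Change of model for end-stage liver disease (MELD) score from baseline to Week 12". The only other Arm 4 endpoint, biliary dilation frequency, belongs to the bile duct objective. The SAP restates the objective and endpoint in 2.3 and 3.2.3. Its analysis in 9.7 is: "For Arm 4, absolute change from baseline 1 in MELD score will be presented for the Safety Analysis Set", with a second table from baseline 2 and a listing. SAP Section 11 lists no change that adds a survival or transplant outcome.

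The events are foreseen. Exclusion 10 lets Arm 4 patients be on an active transplant list. Section 7.2.4.2 ("Patients will be withdrawn in the following circumstances") names both death and liver transplantation. Section 7.2.4.1 also names transplantation, under a different lead-in: "A patient will discontinue dosing but may remain in the study for safety monitoring if any of the following criteria are met".

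On missing values, Section 10.2.2.2 says "In general, imputations of missing observations will not be made" and leaves details to the SAP, which gives none for MELD. On early stopping, Table 1 footnote b says "An EOT visit must be performed as soon as possible after premature drug discontinuation". Table 1 schedules MELD at Visit 2 and at Visit 7 (12 weeks/EOT) only.

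**The concern.** MELD is a function of creatinine, bilirubin and INR. It has no term for death or transplant. A table of mean MELD change therefore cannot say how many Arm 4 patients were alive without a transplant, although it is the only output assigned to that objective.

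The two events also disturb the measure. A patient who has one of them and no EOT MELD is absent from the Week 12 mean. A transplanted patient who does have an EOT MELD may contribute laboratory values produced by the new liver, because no rule excludes them. In either case the mean may look better than the patient's course on treatment would justify. At stake is the reading of one exploratory table in an arm of about six; no test or stated decision depends on it.

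**Working it through.** **1. Figures in the plan.** The only sample figure is 4 arms × 6 = 24, which matches the planned total. No event rate, expected MELD change or SD is stated, so what follows is a reading of the rules plus an illustration.

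**2. What the rules do with each patient.**

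| Course in Arm 4 | Week 12 MELD under the plan |
|---|---|
| Stops drug, has an EOT visit, later dies | EOT value exists and may show the deterioration |
| Dies without an EOT visit | None; not imputed; omitted from the mean |
| Transplanted, only End-of-Study procedures done (Protocol 7.2.4.2) | None scheduled: Visit 8 has neither MELD nor coagulation |
| Transplanted, EOT done afterwards (Protocol 7.1.1, 7.2.4.1, footnote b) | Value from the new liver; not excluded |

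The last row depends on timing. MELD has no row in the SAP 4.5 window tables. Week 12 begins at Day 86 for chemistry and Day 72 for coagulation, each running to seven days after the later of last dose and EOT. With an EOT visit from Day 86, all inputs are Week 12. From Day 72 to 85, INR is Week 12 while creatinine and bilirubin are Week 8. Before Day 72, every input has an earlier label, and which visit the MELD belongs to is undefined. The EOT procedure list in Protocol 7.1.3.3 also omits MELD, although Table 1 includes it.

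**3. Size, using the protocol's formula.** MELD = 9.57 ln(creatinine) + 3.78 ln(bilirubin) + 11.2 ln(INR) + 6.43, with values below 1.0 set to 1.0. All laboratory values here are assumptions.

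- Baseline (creatinine 0.9, bilirubin 3, INR 1.2): 0 + 4.15 + 2.04 + 6.43 = 12.6
- Deteriorated (1.5, 12, 1.8): 3.88 + 9.39 + 6.58 + 6.43 = 26.3, change +13.7
- Post-transplant (1.1, 1.0, 1.1): 0.91 + 0 + 1.07 + 6.43 = 8.4, change −4.2

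Let the other five patients each change by s. The mean is (5s + 13.7)/6 if the deterioration is counted, s if the patient is missing (n = 5), and (5s − 4.2)/6 if the post-transplant value is used.

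| s | Counted | Missing | Post-transplant |
|---|---|---|---|
| −1 | +1.4 | −1.0 | −1.5 |
| 0 | +2.3 | 0.0 | −0.7 |
| +1 | +3.1 | +1.0 | +0.1 |

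The sign changes in some rows and not in others. With s = 0, losing one patient who worsened by 5, 10 or 15 points lowers the six-patient mean by 5/6 = 0.8, 10/6 = 1.7 or 15/6 = 2.5. Transplant-free survival is 5/6 = 83.3% throughout.

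**4. Chance that it arises.** 1 − (1 − p)^6 is 11%, 26%, 47% or 74% for an assumed 12-week risk p of 2%, 5%, 10% or 20%.

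**5. What a direct count would give.** Exact 95% intervals: 6/6, 54.1% to 100%; 5/6, 35.9% to 99.6%; 4/6, 22.3% to 95.7%.

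**The case against.** The strongest reply is that nothing is hidden. SAP 9.1 counts events leading to death and lists deaths. SAP 5.1 tabulates reasons for stopping treatment and study by arm and lists disposition. SAP 9.7 plans a MELD listing, and summaries show n. In an arm of about six a careful reader can find any patient who died or was transplanted. This stands, and it is the main reason the point is minor. It does not close the gap, because none of those outputs is tied to this objective.

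A second reply is that deaths need not be lost: a patient who deteriorates, stops drug and dies later can contribute a poor EOT value. This also stands. The omission applies only where no EOT MELD was obtained.

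Third, the entry limits (INR at most 1.3, no hepatic decompensation) may keep 12-week risk low. That is possible, but inclusion 14 admits worsening obstructive cholestasis and transplant listing, and no rate is given.

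Fourth, with no control arm, neither MELD change nor a proportion out of six can show an effect on survival. That is right. The count would be descriptive, but it would describe the outcome that the objective names.

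**Conclusion.** The mismatch is real and minor. The plan states a transplant-free survival objective, assigns it only change in MELD, and gives no rule for MELD after death or transplant. One event among about six patients could change the sign of the mean. That illustration rests on assumed laboratory values and on the deterioration having been measured.

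A reader might infer more: that the worst outcomes improve the result as a matter of course. The documents do not support that. An omitted patient is not scored as improved; the mean is simply taken over the others. Improvement proper needs a post-transplant value, which clearly enters the Week 12 mean only for a late transplant (EOT from Day 86) and has an undefined label before that. A reader might also infer that deaths go unreported, which the safety and disposition outputs contradict.

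Separately, Protocol 7.2.4.1 and 7.2.4.2 differ on whether a transplanted patient may remain in the study or is withdrawn. The two must be reconciled, because the answer bears on whether an EOT MELD is obtained.

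**What to change.** In SAP 9.7 and Protocol Section 6.2.3:

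1. Under this objective, report the number and percentage of all dosed Arm 4 patients, including any who were replaced, alive without liver transplant through Week 12, with the day of each event. Use the death, AE and discontinuation data already collected. Show patients of unknown status separately, such as those lost to follow-up or stopped after the single dose.
2. Exclude MELD inputs measured after transplant, and footnote the MELD table with the number of deaths and transplants. The last MELD before the event may be listed with the date of its INR. It should not be a main summary: scheduled coagulation is at Visits 1, 3, 5 and 7 only, so after Visit 5 the INR can be up to 98 − 42 = 56 days (8 weeks) old and may miss the deterioration.
3. Label MELD change as a measure of liver disease severity, not of survival.

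The cost is SAP and endpoint wording, one count and one footnote, with no new visits, samples or patients. The downside is imprecision: 5/6 has an exact 95% interval of about 36% to 99.6%, and without a control arm the figure is descriptive only.
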